### 6.1.1. Study Scheme

Each investigator will recruit consecutive patients diagnosed with UC or CD that started biological treatment between June 2011 and June 2013, which fulfill inclusion criteria and give written informed consent. Investigators will inform patients about the study objectives and methodology and will fill in electronic Case Report Forms (eCRF) with sociodemographic and clinical data Figure 1 summarizes the study scheme.

**Figure 1.** Study Scheme

### 6.1.2. Study calendar

The expected calendar is as follows:

Months	1	2	3	4	5	6	7
Field work							
Data management							
Data Analysis							
Report							

**Figure 2.** Study calendar

## 6.2. Investigator recruitment, training and site selection

25 gastroenterology centers, representative from all the Spanish territory will be selected. One investigator (gastroenterologist) per center is expected to participate in the study in order to recruit the estimated sample.

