### 6.2.1. Investigator recruitment

Study sites will be identified and selected across all the Spanish geographies in order to provide patients representativeness of the Spanish population and in order to enable

fulfillment of the objectives of the study. The study will be conducted among hospital- and office-based gastroenterologists specialized in UC and CD care management.

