#### 6.4.3. Data collection

25 gastroenterology centers (one investigator per center) from all around Spain will participate in the study. In order to achieve the minimum sample, each gastroenterology specialist will have 4 months to include approximately 8 UC and 8 CD consecutive patients that fulfill the inclusion/exclusion criteria specified on sections 6.3.2 and 6.3.3. Investigators will inform patients about the study objectives and

methodology and patients will have to give written informed consent before inclusion in the study as specified on section 6.3.5.

Investigators will collect sociodemographic and clinical data from patients' records specified on section 6.4.3 and will introduce it in the eCRF.

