## 7. Statistical Analysis

### 7.1. Sample size calculation

Response to treatment with biologics is estimated at 50%, meaning that half of included patients are expected to be non-responders. Considering a minimal sample of 10 patients that present the event of interest per independent variable included in the logistic regression model and a maximum of 10 independent variables per model, a minimum estimated sample of 200 UC patients and 200 CD patients is required.

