7.2. Primary efficacy endpoint

- **Primary endpoint:** Evaluate the impact of the co-morbidities profile in IBD patients on treatment response to biological therapy.

The analysis that will be performed to answer the objective will be the following:

In order to determine the level of correlation between the co-morbidities profile and treatment response, adjusting for sociodemographic and clinical profile of patients, two logistic regression models will be conducted. The dependent variable of the models will be the **lack of response during the induction phase and the loss of response during the maintenance phase**. In both models independent variables will include all comorbidities, as well as sociodemographic and clinical variables as covariates.

- The following potential variables will be considered for the analysis:
 - Crohn's Disease or Ulcerative Colitis.
 - Myocardial Infarction (yes/no).
 - Congestive Heart Failure (yes/no).
 - Peripheral Vascular Disease (yes/no).
 - Cerebrovascular Disease (yes/no).
 - Dementia (yes/no).
 - Chronic Obstructive Pulmonary Disease (yes/no).
 - Connective Tissue Disease (yes/no).
 - Peptic Ulcer Disease (yes/no).
 - Mild Chronic Hepatopathy (yes/no).
 - Diabetes Mellitus (yes/no).
 - Hemiplegic (yes/no).
 - Moderate-Severe Chronic Kidney Disease (yes/no).
 - Diabetes with lesions in target organs (yes/no).
 - Solid Tumor (yes/no).
 - Leukemia (yes/no).
 - Lymphoma (yes/no).

- Moderate-Severe Chronic Hepatopathy (yes/no).
 - Solid tumor with metastases (yes/no)
 - Acquired immunodeficiency syndrome (AIDS) (yes/no).
 - Gender.
 - Race (caucasian, asiatic, latin, black, other).
 - Level of education (uneducated, primary education, secondary education, university education).
 - Working status (student, self-employed, employed by other, retired, housework, unemployed, temporarily unable to work, permanently unable to work, other).
 - Smoking habits (non-smoker, ex-smoker and smoker).
 - Alcohol abuse (yes/no).
 - Time from diagnostic of disease.
 - Disease location.
 - Discontinuation the biological treatment (yes/no)
- Each one of the variables will be compared between the subjects with primary non-response vs primary response and primary response maintenance vs loss of response and those variables whose p-value is lower than 0.1 are considered potential variables for performing a logistic regression analysis.

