7.3. Secondary efficacy endpoints

- Secondary endpoint: Evaluate the impact of Extraintestinal Manifestations profile in IBD patients on treatment response to biological therapy.

The analysis that will be performed to answer the objective will be the following:

To evaluate the impact of extraintestinal manifestations profile in IBD patients on treatment response to biological therapy, a logistic regression analysis will be performed, in which **lack of response during the induction phase** will be used as the dependent variable and patient disease (CD or UC) and different extraintestinal manifestations variables (arthropathy and arthritis, metabolic bone disease, eye disease, oral, aural and nasal disease, skin disease, hepato-pancreato-biliary disease, neurological disease, cardiovascular manifestations of IBD,

pulmonary manifestations of IBD) will be used as independent variables, yielding the following results: Odds Ratio, 95%CI, p-value, sensitivity and specificity.

We will repeat this analysis with the **loss of response during the maintenance phase variable** as dependent variable.

- **Secondary endpoint: Describe the percentage of IBD patients exhibiting co-morbidities.**

The analysis that will be performed to answer the objective will be the following:

We will provide the frequencies, percentages and 95%CI of the following comorbidities for patients with Crohn's Disease and Ulcerative Colitis separately:

- Myocardial Infarction (yes/no).
- Congestive Heart Failure (yes/no).
- Peripheral Vascular Disease (yes/no).
- Cerebrovascular Disease (yes/no).
- Dementia (yes/no).
- Chronic Obstructive Pulmonary Disease (yes/no).
- Connective Tissue Disease (yes/no).
- Peptic Ulcer Disease (yes/no).
- Mild Chronic Hepatopathy (yes/no).
- Diabetes Mellitus (yes/no).
- Hemiplegic (yes/no).
- Moderate-Severe Chronic Kidney Disease (yes/no).
- Diabetes with lesions in target organs (yes/no).
- Solid Tumor (yes/no).
- Leukemia (yes/no).
- Lymphoma (yes/no).
- Moderate-Severe Chronic Hepatopathy (yes/no).
- Solid tumor with metastases (yes/no)
- Acquired immunodeficiency syndrome (AIDS) (yes/no).

- **Secondary endpoint: Determine the co-morbidities profile according to the level of IBD severity.**

The analysis that will be performed to answer the objective will be the following:

We will classify the patients into IBD severe or non-severe at baseline based on the HBI and PMI scores according the following criteria:

Harvey-Bradshaw Index score

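### No planned interval, test or model accounts for site: comorbidity-percentage intervals are too narrow if comorbidity clusters by site, and site may confound the primary odds ratios

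*Protocol*

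**What the plan says.** Protocol 6.2 plans for a clustered sample: "25 gastroenterology centers, representative from all the Spanish territory will be selected", and "One investigator (gastroenterologist) per center is expected to participate in the study". Protocol 6.4.3 sets the cluster size: "each gastroenterology specialist will have 4 months to include approximately 8 UC and 8 CD consecutive patients". Practice types are mixed, since Protocol 6.2.1 states: "The study will be conducted among hospital- and office-based gastroenterologists specialized in UC and CD care management".

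Response is defined first by a change of at least 2 points in HBI or PMS. Where the index is unavailable, it rests on the physician's own criteria (Protocol 6.4.5, SAP 7.1). With one investigator per centre, site and assessor coincide.

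The analyses affected are these:

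- **Comorbidity percentages.** SAP 7.3 states: "We will provide the frequencies, percentages and 95%CI of the following comorbidities", separately for CD and UC. Neither this section nor Protocol 7.5 names an interval method.
- **Primary objective.** SAP 7.2 states that "two logistic regression models will be conducted". Its candidate list runs from the Charlson items to race, education and working status, with no site, investigator, region or practice type. Screening uses the ordinary chi-squared test and t-test.
- **Extraintestinal-manifestation and severity models.** The models in SAP 7.3 also omit site.

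Site appears in the SAP only in the listing of disposition discrepancies (SAP 4.2). It is recorded for every patient, as the first two digits of the patient code (Protocol 9.1).

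**The concern.** Two separate consequences are possible.

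The first concerns the percentages. Patients from one centre may resemble each other in comorbidity, for example because a hospital clinic and an office practice see different patients. A standard binomial interval treats all 200 patients per disease as independent. For a percentage, within-site correlation inflates the variance in full. Sites are chosen to represent Spain, so the target is wider than these 25 centres.

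The second concerns the primary odds ratios. Comorbidity varies between patients within a site, so clustering alone changes their standard errors little. Confounding is another matter. If centres with more comorbidity also achieve less response, or judge response more strictly, a crude odds ratio absorbs that difference. Mixed practice types and the physician-judgement fallback make this plausible. Investigator training is one phone call (Protocol 6.2.2), and there is no on-site monitoring (Protocol 9.2). Nothing planned would reveal the problem.

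**Working it through.** **Step 1: the plan's own figure.** Protocol 7.1 assumes 50% non-response, "a minimal sample of 10 patients that present the event of interest per independent variable" and at most 10 variables per model. This gives 10 × 10 / 0.5 = 200 per disease, which matches 25 sites × 8 patients = 200. The stated figure reproduces, with no allowance for clustering.

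**Step 2: intervals for percentages.** Cluster size is m = 8 within one disease. The documents give no intraclass correlation (ICC), so 0.01 to 0.10 is an assumed range.

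- Design effect: DE = 1 + (m − 1) × ICC = 1 + 7 × ICC.
- The correct width is the naive width × √DE.
- Actual coverage of a nominal 95% interval is 2Φ(1.96/√DE) − 1.
- Effective sample size is 200/DE.
- At an assumed 10% prevalence the naive half-width is 1.96 × √(0.1 × 0.9/200) = 4.16 points.

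| ICC (assumed) | DE | √DE | Coverage | Effective N | Half-width at 10% |
|---|---|---|---|---|---|
| 0 | 1.00 | 1.000 | 95.0% | 200 | 4.16 |
| 0.01 | 1.07 | 1.034 | 94.2% | 187 | 4.30 |
| 0.02 | 1.14 | 1.068 | 93.4% | 175 | 4.44 |
| 0.05 | 1.35 | 1.162 | 90.8% | 148 | 4.83 |
| 0.10 | 1.70 | 1.304 | 86.7% | 118 | 5.42 |

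Unequal recruitment adds to this. With an assumed coefficient of variation of 0.5 in site size and ICC 0.05, DE = 1 + (1.25 × 8 − 1) × 0.05 = 1.45.

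**Step 3: which ICC is plausible for a rare condition.** A site standard deviation of 0.5 to 0.8 on the logit scale (assumed) corresponds to the following:

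| Prevalence | ICC | Interval should be wider by |
|---|---|---|
| 2% | 0.005–0.016 | 2–5% |
| 5% | 0.013–0.035 | 4–12% |
| 10% | 0.023–0.060 | 8–19% |

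For example, √(1 + 7 × 0.060) = 1.19. An ICC of 0.10 would need a common condition or larger site differences.

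**Step 4: confounding of the odds ratios.** The simulation used 25 sites × 16 patients, 50% non-response and a true within-site odds ratio of 1. Site effects were normal on the logit scale, with SD 0.6 for the outcome and 0.5 to 0.8 for comorbidity. All site parameters are assumed. Site was left out of the crude analysis.

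| Correlation of site effects | Prevalence | Mean crude OR | Type I error |
|---|---|---|---|
| 0.5 | 5% | about 1.13–1.23 | 5–7% |
| 0.5 | 10% | about 1.13–1.23 | 6–12% |
| 0.5 | 20–30% | about 1.13–1.23 | about 10–15% (highest single run 15.6%) |
| 0 | any of these | about 1.00 | 5–7% |

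At 2% prevalence the crude error is only 1 to 2%, because the test is conservative with so few affected patients.

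**Step 5: which adjustment works.** In the same setting with correlation 0.5, stratifying by site gave a mean odds ratio of 0.99 to 1.00 and error of 4 to 6%. A site random intercept left the mean odds ratio at 1.04 (prevalence 10%, SD 0.5), 1.13 (10%, SD 0.8) and 1.10 (30%, SD 0.8), with error of 5.7 to 7.5%. It removes only part of the bias.

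**Step 6: fixed site terms.** These need 25 − 1 = 24 parameters. The protocol's limit is 10 per model. Even pooling both diseases, 400 × 0.5 / 10 allows only 20.

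**The case against.** The strongest counter-argument is that every size above rests on an ICC, site standard deviations and a correlation that the documents do not give. That stands, and it is why the point is conditional. If the ICC is zero the percentage intervals are right, and if site effects on comorbidity and response are unrelated the odds ratios are essentially unbiased.

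It is also fair that the primary models use 19 separate yes/no Charlson items. Several of these, such as dementia, AIDS and metastatic tumour, are likely to be rare in this population (the documents give no prevalences). For rare items both the interval effect and the type I error inflation are small, so the larger figures apply only to common conditions.

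Physician judgement is a fallback and not the main definition of response. This limits the assessor route to confounding without closing it: the data are retrospective and the documents do not say how often an index will be missing. Case-mix differences do not depend on the fallback.

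Finally, SAP 5.1 calls the study descriptive and mainly exploratory, so no decision hangs on a fraction of a percentage point. This lowers the stakes for the percentages. It does not dispose of the primary question, which the plan answers with adjusted odds ratios, p-values and confidence intervals.

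A reader might infer that site is ignored in every part of the plan, that the intervals are certainly too narrow, or that the odds ratios are confounded. The documents support none of these as stated. The SAP does use site in the disposition listing, and nothing in either document shows that comorbidity clusters by site or that site differences in comorbidity and response go together.

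**Conclusion.** The point holds in conditional form. It is established from the documents that no inferential analysis accounts for site, that the design is clustered with one assessor per centre, and that the site code is available for every patient.

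For the percentages, the direction is certain for any positive ICC. The size runs from negligible at 0.01 (3% wider, 94% coverage) to material at 0.05 (16%, 91%) and 0.10 (30%, 87%), with rare conditions more likely at the lower end.

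For the primary odds ratios, bias needs site to be linked to both comorbidity and response. At an assumed correlation of 0.5 a null odds ratio appears as about 1.13 to 1.23, and type I error reaches 10 to 15% only for conditions affecting about 20 to 30% of patients. Without correlation there is no meaningful problem.

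The change is worth making because it is cheap, and because the plan as written could not show whether site matters.

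**What to change.** - **SAP 7.3, comorbidity percentages.** Name the interval method and use a design-based variance with site as the cluster, with a t reference on about 24 degrees of freedom.
- **SAP 7.2, primary models.** Include a site random intercept in both models and report the estimated site variance.
- **SAP 7.2, within-site analysis.** Add a conditional (site-stratified) logistic analysis for comorbidities common enough to estimate, with the minimum frequency stated in advance. This is needed because the random intercept removes only part of any between-site confounding.
- **Avoid 24 fixed site terms.** They exceed the plan's own limit of 10 variables per model.

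The cost is SAP wording; no new data are needed. Intervals become somewhat wider. In the within-site analysis, a site where no patient has the condition, or where all patients have the same response, contributes nothing to that odds ratio. Information is therefore lost for rare comorbidities, and some odds ratios may not be estimable. If the site variance proves close to zero, results will barely change and the report can say so.

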### 6.2.1. Investigator recruitment

Study sites will be identified and selected across all the Spanish geographies in order to provide patients representativeness of the Spanish population and in order to enable

fulfillment of the objectives of the study. The study will be conducted among hospital- and office-based gastroenterologists specialized in UC and CD care management.

#### **6.2.2. Investigator training**

A training phone call will be performed to all participant investigators in order to explain the protocol and to train them and their personnel in the eCRF.

### **6.3. Patient selection**

#### **6.3.1. Study population**

The present study will include patients diagnosed with UC or CD that started biological treatment between June 2011 and June 2013, attending physician gastroenterology services in Spain. In order to avoid a biased sample, investigators will recruit consecutive patients. It is estimated that a period of 4 months will be necessary to achieve the desired sample of 200 UC and 200 CD patients.

#### **6.3.2. Inclusion criteria**

- Adult patients (aged  $\geq 18$ )
- Patients diagnosed with UC or CD according to the "World Gastroenterology Organization Practice Guidelines for the Diagnosis and Management of IBD in 2010"
- Patients naive to biologics that started treatment with biologics between June 2011 and June 2013
- Patients in whose biological treatment was prescribed according to daily clinical practice.
- Patients that gave written informed consent

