#### 6.4.4. Study variables

The following **sociodemographic variables** will be collected from patients' medical records or directly from patients during the study visit, straight after their inclusion in the study:

- Age
- Gender
- Race (caucasian, asiatic, latin, black, other)
- Level of education (uneducated, primary education, secondary education, university education)
- Working status (student, self-employed, employed by other, retired, housework, unemployed, temporarily unable to work, permanently unable to work, other)
- Smoking habits (non-smoker, ex-smoker, smoker, number of cigarettes per day)
- Alcohol intake (units per week).

The following **clinical variables** will be collected from patients' medical records (when available) or directly from patients during the study visit, straight after their inclusion in the study:

- Date of diagnosis (UD or CD).
- Disease activity at the beginning of the reference period and at the study visit through collection of the following variables:
  - For UC patients:
    - Partial Mayo Score (PMS) (9 point scale that excludes the endoscopic appearance of the mucosa)
    - General disease activity:
      - Mild: up to four bloody stools daily and no systemic toxicity
      - Moderate: four to six bloody stools daily and minimal toxicity
      - Severe: more than six bloody stools daily and signs of toxicity, such as fever, tachycardia, anaemia, raised erythrocyte sedimentation rate.
      - Fulminant: More than ten bloody stools daily, continuous bleeding, anaemia requiring blood transfusion, abdominal tenderness and colonic dilatation on plain abdominal radiographs.
    - Disease anatomic extent: proctitis, left-sided colitis or pancolitis.
    - Endoscopy findings:

- Normal or inactive disease
- Mild disease (erythema, decreased vascular pattern, mild friability)
- Moderate disease (marked erythema, lack of vascular pattern, friability erosions)
- Severe disease (spontaneous bleeding, ulceration).
- For CD patients:
  - Harvey-Bradshaw Index (HBI) (a simplified version of CDAI)
  - General disease activity:
    - Mild to moderate: ambulatory patients able to tolerate oral alimentation without manifestations of dehydration, toxicity, abdominal tenderness, painful mass, obstruction or >10% weight loss.

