- Urogenital manifestations of IBDComorbidities in UC and CD patients (defined as the coexistence of another medical condition alongside IBD, and does not imply causation) at the time of diagnosis and at the study visit, will be listed according to chosen according to the Charlson index:

Comorbidity Component	Score
Myocardial Infarction	1
Congestive Heart Failure	1
Peripheral Vascular Disease	1
Cerebrovascular Disease	1
Dementia	1
Chronic Obstructive Pulmonary Disease	1
Connective Tissue Disease	1
Peptic Ulcer Disease	1
Diabetes Mellitus	1 (mild), 2 (moderate- severe)
Moderate-Severe      Chronic      Kidney Disease	2
Hemiplegic	2
Leukemia	2
Malignant Lymphoma	2
Solid Tumor	2 (tumor), 6 (if metastasis)
Liver Disease	1 (mild), 3 (moderate-severe)
Acquired immunodeficiency syndrome (AIDS)	6

- Biological treatment/s for UC or CD followed during the reference period:
  - Starting date
  - Posology
  - Intensification of biological treatment: date and type of intensification
  - Continuing with the treatment
  - Date and reason for discontinuation, if applicable
  - New biological treatment prescribed after discontinuation, starting date, posology, continuing with the treatment, date and reason for discontinuation.
- Concomitant treatment with corticosteroids (e.g. prednisone, hydrocortisone, betamethasone, methylprednisolone, etc,) or immunosuppressives (e.g. Ciclosporin, Methotrexate, etc) during induction phase
  - Starting date, number of cycles

Other treatments followed before the reference period to be chosen from the following list:

- Aminosalicylates (e.g. mesalazine, Sulfasalazine, 5-ASA, etc), oral, enema, suppository.
- Corticosteroids (e.g. prednisone, hydrocortisone, betamethasone, methylprednisolone, etc), oral, enema, suppository.
- Thiopurines (e.g. azathioprine, mercaptopurine, etc).
- Immunosuppressives (e.g. Ciclosporin, Methotrexate, etc).
- Anti-diarrheal drugs.
- Pain medications.
- Antidepressants.
- Antibiotics.
- Use of alternative medicine (e.g. acupuncture, relaxation therapy, Qigong, herbal therapy, etc).
- Other (specify)

- Other treatments followed during the reference period to be chosen from the following list:
  - Aminosalicylates (e.g. mesalazine, Sulfasalazine, 5-ASA, etc), oral, enema, suppository.
  - Corticosteroids (e.g. prednisone, hydrocortisone, betamethasone, methylprednisolone, etc), oral, enema, suppository. Number of cycles
  - Thiopurines (e.g. azathioprine, mercaptopurine, etc).

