#### 6.4.5. Main outcome

Non responders will be those patients not achieving a reduction in HBI of at least 2 points from baseline for CD, and a decrease in the PMS of at least 2 points for UC.. In the cases where these indexes are not available, clinical response will be evaluated according to physician criteria at short term (10 weeks after starting the anti-TNF) and at long term (at least 6 months after starting the anti-TNF). Primary non-responders (PNR) were defined as patients with no clinical response at short term. Loss of response (LOR) was defined as loss of the effect of the drug along the follow up in a patient with initial response.

Reasons to stop the drug will be classified as follows: PNR, LOR, side effects (SE), remission and other.

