7. EFFICACY ASSESSMENT

7.1. Efficacy Assessment; general considerations

Non responders will be those patients not achieving a reduction in HBI of at least 2 points from baseline for CD and a decrease in the PMS of at least 2 points for UC.

In the cases where these indexes are not available, clinical response will be evaluated according to physician criteria at short term (10 weeks after starting the anti-TNF [*primary response and primary non-response*]) and at long term (at least 6 months after starting the anti-TNF [*primary response maintenance and loss of response*]).

We will calculate the following variables:

- **Lack response during the induction phase (primary non response):** Those patients who 10 weeks after starting the anti-TNF not achieving a reduction in HBI of at least 2 points from baseline for CD and a decrease in the PMS of at least 2 points for UC. In the cases where these indexes are not available, clinical response will be evaluated according to physician criteria at short term (*primary response and primary non-response*).
- **Loss of response during the maintenance phase (secondary loss of response):** Those patients who at least 6 months after starting the anti-TNF not achieving a reduction in HBI of at least 2 points from baseline for CD and a decrease in the PMS of at least 2 points for UC. In the cases where these indexes are not available, clinical response will be evaluated according to physician criteria at short term (*primary response maintenance and loss of response*).

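### The reason for starting the first biologic is neither an entry condition nor recorded, so the secondary extraintestinal-manifestation models may be biased toward non-response, by an unknown amount

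*Protocol*

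**What the plan says.** **Eligibility.** Protocol 6.3.2 (repeated in SAP 3.7) takes "Patients naive to biologics that started treatment with biologics between June 2011 and June 2013" and "Patients in whose biological treatment was prescribed according to daily clinical practice". Together with adult age, a UC or CD diagnosis and consent, that is the whole list. Neither it nor the exclusions in 6.3.3 set a minimum activity score or a required indication.

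**Treatment data.** The block headed "Biological treatment/s for UC or CD followed during the reference period" in Protocol 6.4.4 lists start date, posology, intensification, continuation, "Date and reason for discontinuation, if applicable", and any later biologic. It has no field for the reason for starting.

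**Baseline activity.** Protocol 6.4.4 collects "Disease activity at the beginning of the reference period and at the study visit", including PMS for UC and HBI for CD.

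**Response.** Protocol 6.4.5: "Non responders will be those patients not achieving a reduction in HBI of at least 2 points from baseline for CD", with the same 2-point rule on PMS for UC. SAP 7.1 applies it to primary non-response: "Those patients who 10 weeks after starting the anti-TNF not achieving a reduction in HBI of at least 2 points from baseline for CD". Neither document sets a baseline floor. Both fall back on physician judgement where the index is unavailable.

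**Models.** SAP 7.3 regresses primary non-response, then loss of response, on disease type and "different extraintestinal manifestations variables (arthropathy and arthritis, metabolic bone disease, eye disease" and the remaining EIM categories, nine in all. It names no other covariate. The candidate list in SAP 7.2 for the comorbidity models contains neither baseline HBI/PMS nor indication.

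**The concern.** In an EIM model, the reason for prescribing can be the exposure under test. If a biologic was started mainly for joint, skin or eye disease in a patient with little bowel activity, a 2-point fall in HBI or PMS may be unlikely, or impossible, whatever the drug did. Such patients all carry an EIM, so the misclassified outcomes fall among the exposed and push the odds ratio upward. That is the direction the secondary objective would read as an EIM impairing response.

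Baseline scores can show which patients had little room to improve, where the scores were recorded. No listed field lets the analyst recover why the drug was started. As planned, the study could not separate an effect of the EIM from an effect of the prescribing reason.

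**Working it through.** **1. The plan's own figure.** Protocol 7.1 gives 50% non-response, 10 events per variable and at most 10 variables: 10 × 10 / 0.50 = 200 per disease. This reproduces, as does 25 sites × 8 patients = 200. No power or effect size is stated, so there is none to check.

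**2. The floor.** A score of 0 or 1 cannot fall by 2. SAP 7.3 keeps PMS 0-1 (remission) as a baseline category within non-severe, so by the index rule every UC patient in it is a non-responder. The same holds for CD at HBI 0-1. SAP 7.3 calls HBI below 5 remission, but a 2-point fall is possible from 2 to 4. The documents do not say how many such patients are expected.

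**3. Size of the possible bias.** Let f be the share of exposed patients whose biologic was started mainly for the EIM, q their scored non-response, and p0 non-response in everyone else. With no true effect:

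- non-response in the exposed: pe = f × q + (1 − f) × p0
- spurious OR = [pe / (1 − pe)] / [p0 / (1 − p0)]

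Inputs: p0 = 0.50 is from Protocol 7.1. Protocol section 4 gives primary non-response to anti-TNF as up to 30%, so p0 = 0.30 is shown too. The values of f and q are assumptions; the documents give neither.

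Example: f = 0.20, q = 0.80, p0 = 0.50 gives pe = 0.16 + 0.40 = 0.56, and OR = 0.56 / 0.44 = 1.27.

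| f | OR, p0 = 0.50, q = 0.8 to 1.0 | OR, p0 = 0.30, q = 0.8 to 1.0 |
|---|---|---|
| 5% | 1.06-1.11 | 1.12-1.18 |
| 10% | 1.13-1.22 | 1.26-1.37 |
| 20% | 1.27-1.50 | 1.56-1.83 |
| 30% | 1.44-1.86 | 1.91-2.43 |

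If q = p0, then pe = p0 and the OR is 1: the bias needs these patients to be scored as non-responders more often than the rest.

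**4. Chance of a false positive.** This uses the two-proportion normal approximation, two-sided 0.05, 400 pooled patients (SAP 7.3 pools UC and CD with a disease term), p0 = 0.50, q = 0.8 to 1.0 and an assumed EIM prevalence of 10-30%. The chance of a significant result toward non-response is about 4-7% at f = 5%, 6-15% at 10%, 11-45% at 20% and 19-80% at 30%. With no bias, the nominal chance in that direction is 2.5%.

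**5. Room for baseline terms.** The EIM model has 1 disease term and 9 EIM terms. HBI and PMS are different scales, so each needs its own disease-specific term: 10 + 2 = 12. At 10 events per variable, 400 × 0.50 / 10 = 20 terms are supported, and 400 × 0.30 / 10 = 12.

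**The case against.** The strongest reply has five parts.

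- **Response is not judged by the index alone.** Protocol 6.4.5 and SAP 7.1 fall back on physician judgement, and Protocol 6.4.4 lists activity scores only at the start of the reference period and at the study visit, not at 10 weeks. Judgement may therefore decide many primary non-response classifications, and a physician can consider the treated target. This stands: it pulls q toward p0 and shrinks the bias. It does not remove it, because neither document says which target the physician is to judge.
- **Bowel disease was probably the intended indication.** The treatment block refers to UC or CD, section 4 describes biologics in moderate to severe CD and acute severe UC, and the investigators are gastroenterologists. This makes a large f less plausible. None of it is an entry criterion, and the reference to UC or CD can cover a biologic given for an IBD-related manifestation.
- **Baseline scores are collected and may deal with much of it.** This stands as far as the mechanism is low activity at start. A reader might infer that baseline adjustment cannot help because the treated target is never scored. The documents do not list the HBI items, so that cannot be verified for CD. But the planned EIM models contain no baseline term.
- **The primary analysis is barely touched.** A reader might infer that connective tissue disease carries the same bias into the comorbidity models. Protocol 6.4.4 defines a comorbidity as another condition alongside IBD, so a biologic given for it fits poorly under treatment for UC or CD. Large effects also need extreme shares. Suppose 3% of the other patients have connective tissue disease and 2% or 5% of the whole sample were treated for it. Then f = 0.02 / (0.98 × 0.03 + 0.02) = 40%, or 0.05 / (0.95 × 0.03 + 0.05) = 64%. Nothing in the documents supports such shares.
- **Restricting every response model would narrow a daily-practice study.** Protocol section 4 criticises restrictive trial populations. This stands, and it argues for a sensitivity analysis rather than a new main analysis.

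**Conclusion.** The gap is real and limited. Indication is neither required nor recorded, the 2-point rule has no floor, and the EIM models cannot adjust for either. The secondary EIM odds ratios may therefore be biased toward non-response.

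The size cannot be known from the documents. It is negligible to small if about 5% of exposed patients were treated for the EIM (OR 1.06-1.11 at 50% non-response otherwise), and large enough to mislead at 20-30% (1.27-1.86). Only the 50% rate is the plan's; f and q are assumed. The figures describe primary non-response. They carry over to loss of response only as SAP 7.1 words it, with the same 2-point rule.

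Two stronger readings are not supported. One is that the study will report a spurious EIM effect: that depends on f and q, and on how often physician judgement replaces the index. The other is that perianal disease produces the same bias: it appears only as a descriptive CD behaviour subtype in SAP 5.3 and is not an exposure in any planned model, so it could add outcome misclassification but not this bias. For the primary comorbidity models, connective tissue disease is at most a minor route.

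**What to change.** 1. **Protocol 6.4.4, biologic block:** add one chart-derived field: main indication for the first biologic (active luminal disease / perianal or fistulising disease / extraintestinal manifestation / other or not documented).
2. **SAP 7.3:** add baseline HBI and PMS to the EIM models as disease-specific terms. Pre-specify a sensitivity analysis that repeats these models in patients whose biologic was started for active luminal disease.
3. **SAP 7.2:** repeat the comorbidity models in the same subset, also as a sensitivity analysis. The main analysis keeps all daily-practice patients.
4. **SAP 7.1:** state how patients with a baseline HBI or PMS of 0 or 1 are handled, for example counted separately as not evaluable by the index rule.
5. **SAP 4.2:** show the number in each indication category, and the number with a score of 0-1, in the flowchart.

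**Cost.** One extra field, which may be undocumented for some patients treated in 2011-2013, and slightly smaller sensitivity models. If 5%, 10% or 20% of patients were set aside (assumed), 190, 180 or 160 of 200 per disease remain. At 50% non-response that is 95, 90 or 80 events, supporting 9.5, 9 or 8 variables instead of 10. The main analysis is not reduced, so recruitment need not rise. If non-response is nearer 30%, the pooled EIM sensitivity model becomes tight: with 10% set aside, 360 × 0.30 / 10 = 10.8 variables against 12 terms. The SAP should say how rare EIM categories would then be combined.
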